Similar retrospective studies included between 629-1105 patients in their chart review.^{2, 6, 7, 11} Based on the number of vaginal hysterectomies performed by our department annually, we anticipate five years of data collection will provide a comparable study size for this review. Our anticipated sample size will be approximately 800 patients.

Data Collection: Please see attached data collection sheet

- Charts of all patients having a total vaginal hysterectomy by one of our four fellowship trained urogynecologists during the study time frame will be identified and analyzed for inclusion and exclusion criteria.
- All charts meeting inclusion criteria will be included in the analysis.
- Each chart will be reviewed and the following variables collected for analysis:
 - Type(s) of prolapse repair(s)
 - Additional procedure for urinary incontinence at the same time as hysterectomy and prolapse repair – yes/no
 - Preoperative CBC collected within 30 days of surgery – yes/no
 - Preoperative hemoglobin
 - CBC collected the morning of POD1 – yes/no
 - POD1 hemoglobin
 - Change in hemoglobin from preoperative to postoperative collection
 - Change in hemoglobin level ≥ 2 – yes/no
 - Postoperative hemoglobin ≤ 10 – yes/no
 - More than one postoperative hemoglobin obtained – yes/no
 - Patient with objective signs of anemia (*persistent hemodynamic changes: pulse >100 beats per minute, blood pressure <90/60*) – yes/no
 - Patient with subjective signs of anemia (*dizziness, lightheadedness, weakness, pale, cool, diaphoretic*) – yes/no
 - Blood transfusion – yes/no
 - Estimated blood loss
 - IVF volume received intraoperatively
 - Length of surgery (in minutes)
 - Prophylactic heparin given preoperatively – yes/no
 - General demographic data including: name, DOB, age, race, BMI, medical comorbidities, parity, smoking history, menopausal status
 - Preoperative aspirin use – yes/no
 - Preoperative antiplatelet medication use (i.e.: Brilinta, Effient, Plavix) – yes/no
 - Stage of pelvic organ prolapse at preoperative appointment
 - Prior abdominal or pelvic surgery – yes/no
 - Patient readmitted within 30 days of surgery – yes/no

- Patient seen in emergency department within 30 days of surgery – yes/no
- Length of hospital stay (in days)
- Delay in discharge due to CBC results – yes/no

Intervention or experimental aspect of the study:

- No intervention will occur as part of this study.

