- There are no potential risks to the study population by any aspect of this study.

Statistical Analysis:

Demographic data will be described using frequency (percentage) for categorical variables and mean (standard deviation) or median (min, max) for continuous variables. The percentage of subjects with hemoglobin less than 10 g/dL at POD1 will be evaluated as well as the percentage of subjects with signs of anemia. Pearson product moment correlation coefficient will be employed to measure the association between postoperative hemoglobin level and perioperative variables such as age, BMI, blood loss, or length of surgery. The mean hemoglobin change from pre- to postoperative measurement in symptomatic subjects will be compared with that of asymptomatic subjects using Student's t-test. Multiple linear regression will be used to investigate risk factors impacting mean decrease in hemoglobin. On the other hand, multiple logistic regression will be used to investigate factors associated with the presence of signs of anemia.

Ethical Considerations:**Informed Consent:**

- Informed consent will not be required given the retrospective chart review design of this study.

Privacy Information:

- Extensive effort will be made to ensure and maintain participant confidentiality. All identifying information will be maintained in a secure area at all times. All communication between staff members regarding participant data will occur via the Subject ID number only. However, identifying information will be retained in the original/source documents.
- The Excel spreadsheet will be stored on a password protected, encrypted TriHealth computer for ten years following study closure, and then purged.

Cost/Budget:

- This study will incur no cost to the institution, the participants, or the investigators.

Estimated Period of Time to Complete Study	
When will study begin?	Winter 2019
Protocol Development Completed	2 weeks
Admin Review Time	2 weeks
IRB Approval	3 weeks
Data Collection	4 weeks
Data Analysis	2 weeks
Presentation Development (if applicable)	2 weeks
Manuscript Development (if applicable)	4 weeks
Journal Submission Process (if applicable)	4 weeks
Study Closure	2 weeks

When and how will results be disseminated?

- The results will be disseminated by way of an oral or poster presentation at a national meeting and with publication in a high-impact journal.

References:

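### Any woman transfused before the POD1 draw would enter the hemoglobin-change analyses with a treatment-raised value, and the listed variables could not show that this had happened

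*Combined protocol and SAP*

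**What the plan says.** Under Data Collection, the outcome behind the change analyses is listed as "Change in hemoglobin from preoperative to postoperative collection". The only postoperative hemoglobin recorded as a number is "POD1 hemoglobin". Two related items are yes/no only: "CBC collected the morning of POD1 – yes/no" and "More than one postoperative hemoglobin obtained – yes/no". Neither brings with it the value or time of another draw. Transfusion is listed as "Blood transfusion – yes/no", with no date, time or order relative to the draw.

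None of the seven Exclusion Criteria removes transfused women, and Data Collection keeps every eligible chart in the analysis. The Statistical Analysis section then plans the two-group comparison, by t-test: "The mean hemoglobin change from pre- to postoperative measurement in symptomatic subjects will be compared with that of asymptomatic subjects". It adds: "Multiple linear regression will be used to investigate risk factors impacting mean decrease in hemoglobin". It gives no rule for a transfusion that came before the postoperative measurement.

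**The concern.** Transfusion raises hemoglobin. In a woman transfused before the morning draw, the POD1 value reflects both her bleeding and its treatment, so preoperative minus POD1 understates what she lost. She could have bled heavily and still be coded as having no drop of 2 or more.

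The Background describes an overnight stay before the morning CBC, so there is a period in which this could happen. It also argues that nearly every woman who ends up transfused has clinical signs of anemia. On that premise the masked values would collect in the symptomatic group, which may be the small one. The error would then be differential: it would shrink the mean drop in symptomatic women and weaken the regression that looks for risk factors for a larger decrease.

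Timing also bears on the study's purpose, which is to find out whether the routine CBC leads to changes in care. A transfusion given before the routine CBC cannot have resulted from it, and yes/no coding cannot separate the two cases.

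**Working it through.** **The plan's own figure.** Sample Size anticipates about 800 patients, based on case volume and the size of similar studies. No alpha, power, effect size, SD or group split is given, so there is no calculation to reproduce. What follows is a sensitivity calculation.

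**Inputs**
- N = 800 (Sample Size).
- s, symptomatic share: not given for this cohort. In one study cited in the Background, limiting tests to women with two or more signs would have spared 90% of the sample, which implies about 10%. Assumed 10% (80 women), range 5% to 33%.
- t, share transfused before the POD1 draw: not given. The Hypothesis section expects a low overall transfusion rate. Assumed 0.25% to 3%.
- q, share of those women who are symptomatic: nearly all by the Background. Assumed 1, with 0.5 as a check.
- m, hemoglobin masked per affected woman: assumed 1 to 2 g/dL.

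**Formula.** Reduction in the symptomatic-minus-asymptomatic difference in mean drop = m × t × [q/s − (1−q)/(1−s)]. With q = 1 this is (women affected ÷ symptomatic women) × m.

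**Results with s = 10% and q = 1**

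| Women affected (of 800) | m = 1 g/dL | m = 2 g/dL |
|---|---|---|
| 0 | 0 | 0 |
| 2 (0.25%) | 0.025 | 0.05 |
| 4 (0.5%) | 4/80 × 1 = 0.05 | 0.10 |
| 8 (1%) | 0.10 | 8/80 × 2 = 0.20 |
| 16 (2%) | 0.20 | 0.40 |
| 24 (3%) | 0.30 | 0.60 |

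**Dependence on s and q.** With 8 women affected, m = 1 and q = 1, the reduction is 0.20 g/dL at s = 5%, 0.10 at 10%, 0.05 at 20% and 0.03 at 33%. With s = 10% and q = 0.5 it is 0.01 × (0.5/0.1 − 0.5/0.9) = 0.044. Over the whole grid it runs from about 0.002 to 1.2 g/dL. The top of that range needs 24 of only 40 symptomatic women to have been transfused before the draw.

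**Effect on the t-test.** Assume SD 1.2 g/dL, a true difference of 0.5 g/dL, two-sided alpha 0.05 and groups of 80 and 720. The standard error is 1.2 × √(1/80 + 1/720) = 0.141. Power is about 94% with no masking. It is 89% when the contrast shrinks by 0.05, 81% at 0.10 and 56% at 0.20. With a true difference of 0.8 g/dL it is still about 99% at 0.20.

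**Percentage below 10 g/dL at POD1.** If every affected woman were moved above the threshold, the percentage would fall by at most 4/800 = 0.5 to 8/800 = 1.0 percentage point.

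The weakening of the regression coefficients cannot be sized from the documents.

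**The case against.** The strongest reply is that nothing in the documents shows this happened. No section reports a woman transfused before the morning draw, the plan expects few transfusions overall, and only those before the draw matter. That stands, and the point is therefore conditional.

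A reader might also infer any of the following, and the documents do not support them:

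- *That POD1 hemoglobin is the postoperative value for every woman.* Whether a POD1 CBC was drawn is itself a yes/no item, and the plan does not say which value counts when there were several draws. Use of POD1 is the natural reading, because it is the only number listed, but it is still an inference. The data collection sheet that the protocol mentions is not in the text available here and may hold more detail.
- *That the error favours the minimal-utility hypothesis.* The stated goal concerns asymptomatic women, and the argument is that clinical signs identify those who need testing. A smaller contrast makes signs look less informative, which works against that argument. Only the overall percentage below 10 g/dL could move in the hypothesis's favour, and by no more than the small amount worked out above.
- *That the contrast can only shrink.* A woman transfused early might be charted without later signs and counted as asymptomatic. By the formula, the contrast widens only if q is below s, that is, if affected women are less often symptomatic than the cohort as a whole. The Background's premise makes that unlikely but does not exclude it.

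The t-test is one of several analyses and none is named as primary. That limits the weight of the point without closing the gap.

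**Conclusion.** The point holds conditionally. As listed, the plan has no means of recognising or correcting a treatment-raised hemoglobin in the change analyses, and by its own premise the resulting error would fall mainly on symptomatic women. Under the central assumptions the loss is 0.05 to 0.20 g/dL. Against an assumed true difference of 0.5 g/dL that is 10% to 40%, and the upper figure needs 8 affected women, all symptomatic, with 2 g/dL masked in each. None of these inputs except the 800 comes from the documents, so the range is an illustration and not an estimate of bias in this cohort. To say that the contrast is diluted would go too far; it would be diluted if such women exist. With the low transfusion rate that the plan expects, the effect is probably small, unless the symptomatic group is also very small. The case for acting rests on how little the correction costs and on the need to separate transfusions that could have followed the routine CBC from those that could not.

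**What to change.** 1. In each transfused chart, record whether the transfusion came before or after the POD1 draw.
2. For the change t-test, the flag for a drop of 2 or more and the linear regression, take as the postoperative value of a woman transfused before the draw her last postoperative hemoglobin before transfusion, where one exists.
3. Where none exists, as after an intraoperative transfusion, leave her out of the change analyses and report her separately as transfused before the routine CBC.
4. Report these analyses with and without the rule, so that the effect of substitution and omission can be seen.
5. Keep the percentage below 10 g/dL at POD1 as defined, because it describes what the routine test showed. Report beside it the number of women transfused before the draw.

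The cost is a timestamp check in the few transfused charts and a short addition to the Statistical Analysis section. A few values may be lost from the change analyses, and they may belong to women who bled heavily, which is why the separate count and the paired results are needed.

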Date	11/13/2019
Title	Clinical Utility of Postoperative Hemoglobin Testing Following Vaginal Hysterectomy and Reconstruction for Symptomatic Pelvic Organ Prolapse
Principle Investigator	[name]
Sub-Investigators	[name]
Research Specialist	[name], MS
Department	Urogynecology
Hatton #	19-111

Introduction:

- Obtaining a complete blood count (CBC) on post-operative day (POD) 1 to assess postoperative hemoglobin levels is routine practice at our institution after pelvic reconstructive surgery.
- There is minimal data supporting this practice. Multiple studies throughout the gynecology literature suggest that this is not a necessary or cost effective strategy to assess for postoperative anemia. ^{2,6,9,11}
- Most patients who require blood transfusion or reoperation for bleeding will show clinical signs of anemia. ^{2, 6, 7, 11} It is necessary to consider the entire clinical picture before initiating blood transfusion for postoperative anemia. ¹
- Although the individual cost of each lab test is low, the cumulative cost of these tests is substantial. ^{2,9}
- The procedure of choice for prolapse repair by Cincinnati Urogynecology Associates, TriHealth Inc. is a vaginal hysterectomy (TVH) with concurrent apical, anterior, and posterior compartment native tissue repairs as indicated. A review of the literature failed to identify any studies that have looked specifically at the utility of postoperative CBC after vaginal hysterectomy with prolapse repairs.

Purpose of Study

- To determine if checking a routine CBC results in clinically relevant changes to patient care in women undergoing pelvic reconstructive surgery with vaginal hysterectomy for treatment of pelvic organ prolapse.

Hypothesis or Research Question:

- We hypothesize that there is minimal utility in the routine collection of POD1 CBC in patients undergoing TVH during vaginal prolapse repairs.
- We also hypothesize that the overall blood transfusion rate of our pelvic reconstructive patients is low, and that a more selective approach to CBC collection would be appropriate.

Background:

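### No planned analysis shows how many women without signs of anemia have a low POD1 hemoglobin, or which ones, although the study's goal concerns these women

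*Combined protocol and SAP*

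**What the plan says.** The second hypothesis (Hypothesis or Research Question) is that "a more selective approach to CBC collection would be appropriate". The last paragraph of the Background narrows the aim to asymptomatic women after vaginal hysterectomy with prolapse repair.

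The Statistical Analysis section plans five things that bear on this:

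- Two percentages, one for low hemoglobin and one for anemia signs: "The percentage of subjects with hemoglobin less than 10 g/dL at POD1 will be evaluated as well as the percentage of subjects with signs of" (the quote stops one word before the sentence ends).
- Pearson correlations to "measure the association between postoperative hemoglobin level and perioperative variables such as age, BMI, blood loss, or length of surgery".
- A comparison of means: hemoglobin change "in symptomatic subjects will be compared with that of asymptomatic subjects using Student's t-test".
- A linear model: "Multiple linear regression will be used to investigate risk factors impacting mean decrease in hemoglobin".
- A logistic model: "multiple logistic regression will be used to investigate factors associated with the presence of signs of anemia".

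The Data Collection list includes a threshold variable, "Postoperative hemoglobin ≤ 10 – yes/no", and "Blood transfusion – yes/no". It also includes objective signs, subjective signs, preoperative and POD1 hemoglobin, blood loss, length of surgery, BMI and age. The Statistical Analysis section does not mention transfusion.

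**The concern.** Signs are visible without a blood draw. The open question for a selective approach is what the draw would have shown in women who have no signs: how often the value is low, and whether anything known beforehand marks those women out.

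The plan measures both sides of that question but does not join them. Low hemoglobin gets a percentage and signs get a percentage. The only model of a yes/no outcome explains signs. Signs such as dizziness, weakness or a fast pulse may have other causes after surgery, so factors associated with signs need not be factors associated with low hemoglobin. The study could therefore complete every planned analysis and still not report the figure most relevant to its goal.

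**Working it through.** **There is no planned figure to reproduce.** The anticipated 800 women rest on caseload and on the size of similar reviews (629 to 1105). The protocol gives no event rate, effect size or power. All rates below are assumptions, shown over a range.

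**1. What the two separate percentages leave open.** Let a be the proportion with signs and b the proportion with low hemoglobin. The proportion with low hemoglobin and no signs lies between max(0, b − a) and min(b, 1 − a). Dividing by 1 − a gives the range among women without signs. Take N = 800 and a = 10%, so 80 women have signs and 720 do not:

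| Assumed low hemoglobin | Women with low value | Of these, without signs | Share of the 720 |
|---|---|---|---|
| 5% | 40 | 0 to 40 | 0% to 5.6% |
| 10% | 80 | 0 to 80 | 0% to 11.1% |
| 20% | 160 | 80 to 160 | 11.1% to 22.2% |

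The planned percentages alone cannot narrow these ranges.

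**2. What a cross-tabulation would give.** If 10% of the 720 women without signs have a low value, the 95% half-width is 1.96 × √(0.10 × 0.90 / 720) = 2.2 percentage points. If none of the 720 is transfused, the one-sided 95% upper limit is 1 − 0.05^(1/720) = 0.42%.

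**3. Whether a logistic model for low hemoglobin is feasible.** Events = 800 × rate. Supported parameters = events / 10, or events / 20 on a stricter rule.

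| Assumed low hemoglobin | Events | Parameters at 10 each | Parameters at 20 each |
|---|---|---|---|
| 5% | 40 | 4 | 2 |
| 10% | 80 | 8 | 4 |
| 20% | 160 | 16 | 8 |
| 30% | 240 | 24 | 12 |

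Six predictors at 10 events each need 60 events, a rate of 60/800 = 7.5%. Transfusion at an assumed 0.5% to 3% gives only 4 to 24 events, which suits a table but mostly not a model.

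**4. How far the planned models could stand in.** An illustrative simulation used 200 runs of 800 women, each validated on 5000. It assumed preoperative hemoglobin with mean 13.3 and SD 1.1 g/dL, a mean fall of 2.0, about 16% below 10 g/dL, and 11% to 16% with signs. The measure is the area under the ROC curve (AUC) for hemoglobin below 10 among women without signs.

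| Log odds ratio of signs per 1 g/dL lower hemoglobin | Logistic on signs | Logistic on low hemoglobin | Linear on decrease, combined with preoperative hemoglobin |
|---|---|---|---|
| 0 | 0.50 | 0.90 | 0.90 |
| 0.25 | 0.63 | 0.90 | 0.90 |
| 0.5 | 0.72 | 0.90 | 0.90 |
| 1.0 | 0.81 | 0.90 | 0.90 |

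The signs model ranges from uninformative to a moderate proxy, depending on how closely signs follow hemoglobin. The planned linear model carries the information if its prediction is combined with preoperative hemoglobin, a step that the section does not describe.

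**The case against.** The strongest reply is that the plan already looks for hemoglobin risk factors. The two regressions form a deliberate pair, one for hemoglobin and one for signs, with correlations and a t-test beside them. Keeping hemoglobin continuous is also more efficient than cutting it at 10. This stands, and it rules out two stronger readings.

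First, a reader might infer that the plan would miss important factors. Take a factor present in half of 800 women, with low hemoglobin in 15% without it and 26.1% with it. Suppose signs occur in 10% of women with a normal value and 15% of those with a low one. The factor then has about 6% power in the signs model, against about 97% in a model for low hemoglobin. That contrast leaves out the planned linear regression. With normal hemoglobin and the factor acting through the drop, 15% and 26.1% correspond to z = −1.036 and −0.640, a shift of 0.40 SD. With 400 v 400, 0.396 × √(400/2) = 5.60, and 5.60 − 1.96 = 3.64, so power exceeds 99.9%. If the standardized effect is 20% smaller, power is still about 99%. The plan would find such a factor.

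Second, a reader might take the signs model as the intended selection rule. The protocol says only that it will look for associated factors. It sets no trigger for a CBC and builds no score. The two-sign criterion in the Background belongs to a cited study.

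The Background also reports that almost all women who need transfusion show signs. That bears on transfusion in other surgical populations, and the protocol itself says that this population has not been studied. It is a reason to tabulate signs against transfusion here.

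What the reply does not meet is the missing link at the threshold. A mean difference, a correlation or a regression slope for the decrease does not report how many women without signs fall below 10 g/dL.

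**Conclusion.** The point holds as a gap in the analysis plan. The goal concerns asymptomatic women, and no planned analysis relates signs or other predictors to low hemoglobin at the threshold that the plan itself names. That the table, the low-hemoglobin model and any use of transfusion are absent is read directly from the Statistical Analysis section and rests on no assumed rate.

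The size is illustrative. With 10% signs and 5% to 20% low hemoglobin, the planned percentages leave the key proportion uncertain by 5.6 to 11.1 percentage points, whereas a cross-tabulation would estimate it to within about 2 points.

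It would go too far to say that the plan cannot identify these women. The signs model may be a partial proxy, and the linear model with preoperative hemoglobin could predict low values well. The change is worth making because it reports the needed figure directly; it does not make the existing models invalid.

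**What to change.** In the Statistical Analysis section:

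1. Cross-tabulate signs (yes/no) by low POD1 hemoglobin and by transfusion, with confidence intervals. Report the proportion with low hemoglobin among women without signs.
2. Add a logistic model with low POD1 hemoglobin as the outcome and predictors known before the draw: signs, preoperative hemoglobin, blood loss, length of surgery, BMI and age. Fix the order of priority in advance and limit the number to what the events allow, for example about 4 at 40 events. Repeat it among women without signs where events permit. The Data Collection list gives no time window for signs, so state that those used as a predictor were charted before the draw.
3. Keep the linear model as planned, and keep the logistic model for signs as secondary.
4. Use one definition of low hemoglobin. The Statistical Analysis section uses less than 10 and the Data Collection list uses 10 or less, so a value of exactly 10 is classed differently. Reconcile them before analysis.

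The cost is one table and one model, from variables already listed for collection. Dichotomizing loses some information, which is why the linear model stays. If low hemoglobin is uncommon, the model will carry few predictors and the table will be the main result.
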